3.6 Participant Withdrawal and Replacement

Participants may be automatically replaced if they withdraw/discontinue after randomization but prior to any dosing. Replacement of participants who withdraw/discontinue post dose will be at the discretion of the Sponsor. Procedures will be performed according to the site’s SOP.

If a participant is replaced, the replacement participant will receive the same treatment assigned to the original participant and will be assigned a randomization number which reflects the original participant’s randomization number plus 100 (e.g., a participant assigned to randomization number 11001 would be replaced by a participant assigned to randomization number 11101).

This document is confidential.

4. Endpoints

4.1 Part 1a (SAD)

4.1.1 Primary Endpoints

- Changes from baseline in vital signs, electrocardiograms (ECGs), clinical laboratory tests, telemetry, physical examination, neurological examination, Columbia Suicide Severity Rating Scale (C-SSRS), and the overall incidence of AEs and serious adverse events (SAEs).

4.1.2 Secondary Endpoints

- Area under the concentration time curve from time zero to time of last observed concentration (AUC_{0-t}), area under the concentration-time curve from time zero to infinity (extrapolated) ($AUC_{0-\infty}$), maximum plasma concentration (C_{max}), time to maximum plasma concentration (T_{max}), terminal elimination rate constant (λ_z), and terminal elimination half-life ($t_{1/2 el}$).
- Concentrations of ATH-399A and identification of its major metabolites in blood and urine.

4.2 Part 1b (Food Effect)

4.2.1 Primary Endpoints

- Changes from baseline in vital signs, ECGs, clinical laboratory tests, telemetry, physical examination, neurological examination, C-SSRS, and the overall incidence of AEs and SAEs.

4.2.2 Secondary Endpoints

- AUC_{0-t} , $AUC_{0-\infty}$, C_{max} , T_{max} , λ_z , and $t_{1/2 el}$.

4.3 Part 2 (MAD)

4.3.1 Primary Endpoints

- Changes from baseline in vital signs, ECGs, clinical laboratory tests, telemetry, physical examination, neurological examination, C-SSRS, and the overall incidence of AEs and SAEs.

4.3.2 Secondary Endpoints

- AUC_{0-t} , $AUC_{0-\infty}$, C_{max} , C_{max} at steady-state ($C_{max ss}$), minimum plasma concentration (C_{min}), average plasma concentration (C_{avg}), T_{max} , T_{max} at steady-state ($T_{max ss}$), area under the curve for the defined dosing interval (AUC_{0-t} [AUC_{0-24} , Day 12 dose]), AUC_{0-24} (Day 1 dose), λ_z , $t_{1/2 el}$, and accumulation ratio (AR).

5. Analysis Populations

All participants' inclusion status into each analysis population will be determined after database lock but prior to unblinding. Participants will be analyzed according to the treatment received.

This document is confidential.

5.1 Safety Population

The safety population will include all participants who receive at least one dose of study drug (active or placebo). The safety population will be used for all safety and tolerability summaries and analyses.

5.2 Pharmacokinetic (PK) Population

The PK population will include all participants who receive at least one dose of ATH-399A and provide at least one plasma or urine concentration measure.

In addition, any participant with a protocol deviation or AE deemed to affect PK may be excluded from the PK population. Participants may also be excluded from the PK population based upon the following: inclusion and exclusion criteria, acceptable times for visit dates and measurements, compliance with treatment, the nature and quality of the data, and withdrawal. Before the final analysis, the pharmacokineticist, in agreement with the Sponsor, will make the final decision of which participants will be included in the PK population, based on the datasets received.

6. General Aspects for Statistical Analysis

6.1 General Methods

SAS for Windows software will be used to perform all statistical analyses. All relevant data in the database will be presented in the data listings. Unless otherwise stated, all listings will be sorted by study part, treatment, participant number, and assessment date/time. For the purposes of the summary tables, all participants randomized to placebo will be pooled into a single placebo group (i.e., All placebo). Unless otherwise stated, there will also be an overall section for all ATH-399A doses combined (i.e., All ATH-399A). All summaries will be presented separately for each study part. Unless otherwise stated, the descriptions of the analyses which follow apply to all study parts.

The following labels for treatment will be used on all tabulations where the results are displayed by treatment or sequence, in the following order:

Part 1a:

- All Placebo
- ATH-399A 5 mg
- ATH-399A 10 mg
- ATH-399A 20 mg
- ATH-399A 40 mg
- ATH-399A 80 mg
- All ATH-399A

Part 1b:

- Treatment A (Fed)
- Treatment B (Fasted)

or

This document is confidential.

- Sequence AB
- Sequence BA

Part 2:

- All Placebo
- ATH-399A TBD mg
- ATH-399A TBD mg
- ATH-399A TBD mg
- All ATH-399A

6.2 Summary Statistics:

Unless otherwise stated, continuous variables will be summarized using the number of observations (n), and the statistics mean, median, standard deviation (SD), minimum (min) and maximum (max). The min and max values will be presented to the same number of decimal places as recorded in the eCRF, mean and median will be presented to one more decimal place than the raw data, and the SD will be presented to two more decimal places than the raw data.

Summaries of change from baseline variables will include only participants who have both a baseline value and corresponding value at the timepoint of interest. Categorical and binary variables will be summarized with frequency counts and percentages. Percentages will be rounded to one decimal place, with the denominator being the number of participants (N) in the relevant population, unless otherwise stated.

All digits will be used for PK and statistical calculations. For PK tables and listings, the final reportable results or data will be presented by rounding off to two decimal digits, except for the following situations (this applies to individual data and descriptive statistics):

- Terminal elimination rate constant (λ_z) data shall be rounded off to four decimal places.
- PK parameters related to time, such as time of maximum observed concentration (T_{max}) must be reported with the same precision as the actual sampling time, rounded to three decimal places.
- Concentration versus time data, as well as maximum observed concentration (C_{max}) shall be reported as they appear in the corresponding dataset.
- Ratios and 90% CIs, intra- and inter-participant coefficients of variation (CV), and CV (%) will be presented to two decimal places.

Only data from protocol scheduled (“nominal”) visits will be included in the summary tables. Data from unscheduled visits will not be included in the summary tables (unless they were used as baseline) but will be included in the listings.

This document is confidential.

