7 STUDY DESIGN

7.1 Overall Design

This study is a randomized, Phase 1 three-part study:

- Part 1a is a placebo-controlled, double-blind, SAD, safety, tolerability, and PK evaluation of ATH-399A.
- Part 1b is an open-label, single dose, food-effect, safety, tolerability, and PK evaluation of ATH-399A.
- Part 2 is a placebo-controlled, double-blind, MAD, safety, tolerability, and PK evaluation of ATH-399A, in 2 different age groups.

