Blood samples for PK will be collected pre-dose and at specified time points up to 96 hours post-Day 12 dose. Vital signs, ECG, telemetry, safety lab (including drug screen, cotinine, and alcohol breath test), C-SSRS, and physical and neurologic examinations will be performed at specified times. AEs will be recorded throughout the study. For details regarding the timing of specific procedures see [Table 3](#).

Additional Cohort: Following assessment of MAD dosing in participants, an additional cohort of approximately 8 participants will be evaluated at a dose level determined to be safe by the SRC. After assessing eligibility during the 4-week screening period, 8 participants (approximately equal numbers of males and females, with a minimum of 2 of each gender), aged >55-80 years, inclusive, will be enrolled. The study drug will be administered once daily (QD) in the fasted state for a total of twelve (12) consecutive days. On Days 1 and 12, participants will fast for a minimum of 10 hours prior to dosing and 4 hours following dosing. From Days 2 to 11, participants will fast for a minimum of 2 hours prior to dosing and 2 hours following dosing. Six participants will receive ATH-399A and 2 participants will receive placebo once daily (QD).

Eligible participants in this additional cohort will come to the clinical unit on the day before the first study drug administration (Day -1), for baseline assessments and to confirm eligibility and will stay in the clinical unit for 14 days (13 nights), from Day -1 until Day 13.

Blood samples for PK will be collected pre-dose and at specified time points up to 96 hours post-Day 12 dose. Vital signs, ECG, telemetry, safety lab (including drug screen, cotinine, and alcohol breath test), C-SSRS, and physical and neurologic examinations will be performed at specified times. Adverse events will be recorded throughout the study. Participants will return to the clinical unit for outpatient PK blood sample collections on Day 15 (72 hours post-last dose), and Day 16 (96 hours post-last dose) as well as an outpatient follow-up visit that will take place 7 days after receiving the last dose of study drug, on Day 19 (between Day 19 and Day 22). For details regarding the timing of specific procedures see [Table 3](#).

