asthma with no hospitalizations or recurrence in adulthood are permitted to enroll. For the additional cohort in Part 2, any of the above are acceptable where the condition is stable for >6 months and, in the opinion of the Investigator, it does not impact participant safety.

20. A clinically significant abnormality on physical examination, neurological examination, ECG, or laboratory evaluations at screening and Day -1.
21. A QT interval measurement corrected according to the Fridericia rule (QTcF) > 450 msec during controlled rest at screening and Day -1, or family history of long QT syndrome.
22. Any clinically significant abnormalities in rhythm, conduction, or morphology of the resting ECG and any abnormalities in the 12-lead ECG that, in the judgement of the Investigator or Medical Monitor, may interfere with the interpretation of QTc interval changes, including abnormal ST-T-wave morphology or left ventricular hypertrophy.
 - a) PR (PQ) interval shortening < 120 msec (PR < 120 msec but > 110 msec is acceptable if there is no evidence of ventricular pre-excitation).
 - b) PR (PQ) interval prolongation (>220 msec), intermittent second-degree (Wenckebach block while asleep or in deep rest is not exclusionary) or third-degree AV block.
 - c) Persistent or intermittent complete bundle branch block (BBB), incomplete bundle branch block (IBBB), or intraventricular conduction delay (IVCD) with QRS > 120 msec.

Note: at the Investigator's discretion, if an abnormal ECG is observed, the assessment may be repeated.
23. A clinically significant vital sign abnormality at screening or between screening and first dose administration. This includes, but is not limited to, the following in the supine position:
 - a) systolic blood pressure < 90 or > 140 mmHg,
 - b) diastolic blood pressure < 50 or > 90 mmHg, or
 - c) heart rate < 45 or > 100 beats per minute.
 - d) decrease in systolic blood pressure of 20 mmHg or higher, decrease in diastolic blood pressure of 10 mmHg or higher, or increase in heart rate of 30 bpm or higher within 2 to 3 minutes after passing from a supine to a standing position.

Note: at the Investigator's discretion, if a single abnormal vital sign is observed, the assessment may be repeated.
24. Significant (> 5%) weight loss or gain within 30 days prior to screening or between screening and first dose administration.
25. A history of seizures. Occurrence of a single febrile seizure is not exclusionary.

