12.2 General Considerations

All collected data will be reported using summary tables and figures, as appropriate. Data summaries will be presented separately by part, dose, cohort, and overall. Tabulations will be produced for appropriate disposition, demographic, baseline, safety, and PK parameters. Categorical variables will be summarized by frequency distributions (number and percentages of participants) and continuous variables will be summarized by descriptive statistics (mean, standard deviation, median, minimum, and maximum). As appropriate, a 95% confidence interval (CI) will be presented. Graphical displays will be presented, as appropriate. All data will be provided in by-participant listings.

Baseline is defined as the last value prior to the first dose and will be flagged for all necessary analyses.

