8.6 Assessment of Food Effect

To assess the food effect on ATH-399A exposure in Part 1b, the values of AUC_{0-t} , $AUC_{0-\infty}$, and C_{max} calculated for the two diet regimens (fed and fasted) will be evaluated by ANOVA, with terms for sequence, period, and treatment as fixed effects and participant within sequence as a random effect. The exposure measurements ($AUCs$ and C_{max}) will be natural log-transformed prior to analysis. The model will be fitted using restricted maximum likelihood and the Kenward-Roger degrees of freedom approximation. [Error! Bookmark not defined.](#)

The 90% CI for the ratio of the geometric means for AUC_{0-t} , $AUC_{0-\infty}$, and C_{max} obtained between the fed and fasted conditions will be calculated. The absence of a food effect will be concluded when the 90% CI for the ratio of means (geometric means based on log transformed data) of fed and fasted conditions fall within 80% - 125% for AUC_{0-t} , $AUC_{0-\infty}$, and C_{max} .

The SAS code for the analysis model for ANOVA will follow the format given below (using the Mixed Procedure to fit the linear regression). The input variables, datasets, and labels are depicted in italicized red text and have been given generic names.

```
proc mixed data= dataset;
  class participant treatment sequence period;
  model var = treatment sequence period / solution ddfm= KR;
  random participant(sequence);
  lsmeans treatment / cl alpha= 0.1;
  estimate 'fed vs fasting' treatment 1 -1 / cl alpha= 0.1;
  ods output estimates = estimates covparms = covparms;
run;
```

Intra- and inter-participant CV% will also be estimated.

9. Pharmacodynamic (PD) Analyses

There will be no PD analyses for this study.

This document is confidential.

10. Safety

Safety and tolerability analysis will be performed for all participants in the safety population. No inferential statistical analysis of safety data is planned. For Parts 1a and 2, summary tables will be presented by dose (study drug and placebo) and by study drug overall. For Part 1b, summary tables will be presented by treatment and overall.

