10.8 Columbia-Suicide Severity Rating Scale (C-SSRS)

The results of C-SSRS assessments will be listed by participant, and the change in responses to questions on suicidal ideation and behavior will be summarized by treatment.

11. Changes from Analysis Planned in the Protocol

No changes were made to planned analyses.

12. Programming Considerations

All TFLs and statistical analyses will be generated using SAS for Windows, release 9.4 (SAS Institute Inc., Cary, NC, USA) software in accordance with Food and Drug Administration (FDA) guidelines. Phoenix WinNonlin, version 8.3.4 (Certara USA, Inc., Princeton, NJ) will be used for all PK analyses. This software was validated by [REDACTED] in compliance with US 21 CFR Part 11 regulation.

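### Part 2 baseline and safety tables pool placebo across the 18-55 and >55-80 year cohorts and are keyed by dose, not cohort as the protocol asks, so the older active column sits beside a placebo column that is two-thirds younger

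*SAP*

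**What the plan says.** **Design.** Protocol 7.1 describes Part 2 as a "MAD, safety, tolerability, and PK evaluation of ATH-399A, in 2 different age groups". Protocol 7.1.3 has two sequential cohorts of 8 aged 18-55 and an additional cohort of 8 aged >55-80, each with 6 on ATH-399A and 2 on placebo. The dose of the additional cohort is open: it "will be evaluated at a dose level determined to be safe by the SRC".

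**Different entry rules.** Exclusion criterion 19 (Protocol 8.2) lists clinically significant abnormalities by organ system. For the additional cohort only, "any of the above are acceptable where the condition is stable for >6 months" and the Investigator sees no impact on safety. Protocol 9.11 lets this cohort stay on stable antihypertensives, thyroid medication, NSAIDs, proton pump inhibitors and several other classes that it prohibits at 18-55.

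**Tables.** SAP 6.1 states that for summary tables "all participants randomized to placebo will be pooled into a single placebo group (i.e., All placebo". The pooling stays within a part: "All summaries will be presented separately for each study part". The Part 2 labels are All Placebo, three ATH-399A rows with the dose to be determined, and All ATH-399A; none names an age group or cohort. SAP 10 adds: "For Parts 1a and 2, summary tables will be presented by dose (study drug and placebo) and by study drug overall". SAP 7.4 says the same for demographics and baseline.

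**Protocol rule.** Protocol 12.2: "Data summaries will be presented separately by part, dose, cohort, and overall". Protocol 12.3 lists cohort among the keys for baseline characteristics, and Protocol 12.5 does so for PK parameters, where SAP 8 has study part and treatment. SAP 11: "No changes were made to planned analyses".

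**The concern.** Safety and tolerability are the primary objective of Part 2, and the analysis is descriptive, so these tables are the primary result. Protocol 5.2 says the older cohort is there to match the approximate age range of the target population. It differs from the other two cohorts in age, permitted conditions and permitted medication, and it randomises its own two placebo participants.

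A reader of the Part 2 tables will compare the older active column with the only placebo column shown. If background adverse events, shift categories or changes from baseline differ by age group, part of that difference will look like a drug effect in the older column, and part will appear with the opposite sign in the younger columns. The table would not show that this had happened.

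**Working it through.** **1. The plan's own total.** Part 1a 40 + Part 1b 12 + Part 2 aged 18-55 16 + additional cohort 8 = 76, as stated in the protocol synopsis and SAP 3.1. Cohort sizes are empirical, so there is no power calculation to reproduce.

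**2. Age mix of the Part 2 columns** (planned numbers, Protocol 7.1.3 and SAP Table 3.3-2).

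| Column | 18-55 | >55-80 | Younger share |
|---|---|---|---|
| All Placebo | 2 × 2 = 4 | 2 | 4/6 = 66.7% |
| All ATH-399A | 2 × 6 = 12 | 6 | 12/18 = 66.7% |
| Older active column | 0 | 6 | 0% |
| Each younger active column | 6 | 0 | 100% |

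The overall active-versus-placebo contrast is balanced on age. The single-cohort columns are not.

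**3. Size of the distortion.** Let the placebo outcome be y in the younger and y + d in the older group. Pooled placebo = [4y + 2(y + d)]/6 = y + d/3.

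- Older column, inert drug: (y + d) − (y + d/3) = 2d/3 = 0.67d.
- Younger column, inert drug: y − (y + d/3) = −d/3 = −0.33d.

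The documents give no background rates, so d is an assumption:

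| Assumed d (points) | Older column, apparent excess | Younger columns |
|---|---|---|
| 10 | 6.7 | −3.3 |
| 20 | 13.3 | −6.7 |
| 30 | 20.0 | −10.0 |

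For example, with 10% in younger and 30% in older participants, pooled placebo is (4 × 10% + 2 × 30%)/6 = 16.7%, and 30% − 16.7% = 13.3 points.

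**4. Precision of an age-specific placebo column.** With 0 events in n, the two-sided 95% Clopper-Pearson upper limit is 1 − 0.025^(1/n): 84.2% for n = 2 and 45.9% for n = 6.

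As estimates of the older placebo rate under the same 10%/30% assumption:

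- Pooled column: bias 13.3 points; SD = √(4 × 0.09 + 2 × 0.21)/6 = √0.78/6 = 14.7 points; RMSE = √(13.3² + 14.7²) ≈ 19.9 points.
- Two-person column: no bias; SD = √(0.21/2) = 32.4 points, which is also its RMSE.

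**5. If a dose repeats.** A table or model keyed only on dose would then put 6 younger and 6 older active participants in one group. SAP 8.4 and 8.5 enter dose as a class variable with no cohort term. The trough model and the per-dose Day 12/Day 1 ratios would therefore mix the age groups at that dose.

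**The case against.** **Safety is descriptive and the data are kept.** This stands. SAP 10 plans no inferential safety analysis, and the PK models use active participants only, so the placebo pooling enters no test or decision rule. A reader might infer that the older cohort loses its control. The documents do not support that: SAP 3.4 gives Cohort 3 its own randomisation numbers, beginning 23, and the data are listed by participant. What is missing is the summary.

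**Change from baseline removes age differences.** Largely so for stable differences in level, since SAP 10.3 to 10.5 summarise changes and shifts. Differences in adverse event rate, shift category or the change itself are not removed, and observed values are tabulated too.

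**The populations are not so different.** Partly right. The requirement to be healthy and the ECG and vital-sign exclusions apply to both age groups; the contrast comes from age, criterion 19 and permitted medication.

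**The SAP does keep cohorts apart.** In part. Disposition (SAP 7.1) is by cohort. Three active labels match three cohorts, and the sample code in SAP 8.5 has three dose rows, so a separate older active column seems intended. It would be wrong to read the plan as certain to merge active participants across ages; that needs a repeated dose, which the documents leave open. The table shells are a separate document and may settle the labels.

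**Protocol 12.4 asks only for tabulation by treatment, and no objective names an age-specific contrast.** Both are true. But Protocol 12.2 applies generally, and Protocol 12.3 names cohort for baseline tables.

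**A column of two is worse than the pooled one.** On the RMSE figures above it is the noisier estimate. That is a sound reason not to replace the pooled column. It is no reason to withhold the split, because a reader can see that n = 2 but cannot see the age mix of All Placebo.

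**Conclusion.** The point holds as one of presentation and of consistency between the two documents. In the Part 2 baseline and safety tables the older active column is set beside a placebo column that is two-thirds younger. An age difference d would distort that descriptive comparison by 0.67d, and the younger columns by 0.33d in the opposite direction. The fractions are exact for the planned 4 + 2 placebo participants; d itself is unknown, and the example rates are assumptions.

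Pooling the two 18-55 cohorts is reasonable because they share entry rules; that argument does not extend to the older cohort. Whatever one thinks of pooling, the SAP drops a cohort view that Protocol 12.2 and 12.3 require while declaring no change.

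The documents do not support going further and calling the Part 2 safety conclusion biased, since the overall contrast is age-balanced and nothing is tested. Merging of active participants, in the tables and in SAP 8.4 and 8.5, arises only if the older cohort's dose repeats a younger one.

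**What to change.** 1. In SAP 6.1, 7.4 and 10, for Part 2, keep All Placebo and All ATH-399A as overall columns. Add Placebo 18-55 y (n=4) and Placebo >55-80 y (n=2).
2. Label each Part 2 active column by cohort and age group as well as dose, so that a shared dose cannot merge them.
3. Key the Part 2 PK summaries in SAP 8, and the class-variable models in SAP 8.4 and 8.5, by cohort.
4. With these changes the SAP agrees with Protocol 12.2. If they are not made, record the departure and its reason in SAP 11.

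Cost: SAP and shell wording, and two more columns (seven against five), with no new data. The n=2 column is very imprecise and should be read next to the pooled column; a table footnote should say so.
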